## **11.0 STUDY PARAMETERS AND CALENDAR**

### **11.1 Study Parameters**

#### **11.1.1 Screening Evaluation (Consent signing to Day -4) & Baseline period (Day -17 to day -3)**

1. A complete history and physical examination within 30 days prior to study entry.
2. A whole blood sample (10 ML) that will be used for next generation targeted deep sequencing of genes that are common in myeloid malignancies
3. Hematology exam (Appendix VI)
4. Serum Chemistry (Appendix VI)
5. Bone marrow biopsy and aspiration with conventional cytogenetic analysis within 30 days prior to start the study. 10 ML of whole blood or bone marrow aspirate whichever available will be collected in extra lab tube.
6. Documentation of transfusion frequency (PRBC and platelets only) prior to first cycle and prior to each additional cycle

7. Documentation of all medication including multivitamins and other over the counter medications
8. Dates of multivitamin/vitamin C discontinuation must be documented and occur before first dose of study drug. Pre-study laboratory tests must be obtained within 14 days of registration.
9. MDS Response Assessment, assessed by the treating physician

#### **Treatment Period (Day -3 to C6D28)**

1. Hematology exams (Appendix VI) at the start of each cycle (day 1) and the last day of cycle 6 (C6D28)
2. Serum Chemistry (Appendix VI), including Creatinine, bilirubin, ALT or AST at the start of each cycle (day 1)
3. Bone marrow aspirate and/or biopsy to confirm response, to be performed at the end of cycle 6. 10 ML of whole blood or bone marrow aspirate whichever available will be collected in extra lab tube. All bone marrows samples are to be stored at Cleveland Clinic
4. Conventional cytogenetics to be performed at the end of cycle 6
5. Documentation of frequency of transfusions (only PRBC and Platelets) prior to start of each new cycle.
6. Documentation in the medical record of any grade 2 or higher adverse events at each visit. For guidelines on SAE Reporting and AE entry for Case Report
7. Documentation of any prior administration of growth factors and ESA prior to start of each cycle
8. A 10 ML blood sample that will be used for next generation targeted deep sequencing of genes that are common in myeloid malignancies

9. Physical exam and ECOG performance status occurring at the end of each cycle
10. Vital signs occulting at each visit
11. Pregnancy test if applicable
12. MDS Response Assessment, assessed by the treating physician occurring at the end of cycle 6 or EOT, whichever occurs first.
13. Methylation panel only occurring in Cycle 1
14. Azacitidine will be administered intravenously or subcutaneously at a fixed dose of 75mg/m^2/day for 7 consecutive days, (allowing interruptions for weekends, and holidays, of each 28-day cycle).
15. Ascorbic acid will be administered orally daily at 1 g/day three days prior to start azacitidine and then continues daily for a total of 28 days of each 28 days cycle.

#### **Extended Treatment Period (Cycles 7+)**

1. Documentation of frequency of transfusions (only PRBC and Platelets) prior to start of each new cycle
2. Documentation in the medical record of any grade 3 or higher adverse events at each visit. For guidelines on SAE Reporting and AE entry for Case Report
3. Physical exams and ECOG performance status occurring at the end of each cycle
4. Vital Signs at each visit
5. Hematology exams (Appendix VI) at the start of each cycle (day 1)
6. Serum Chemistry (Appendix VI), including Creatinine, bilirubin, ALT or AST at the start of each cycle (day 1).
7. Azacitidine will be administered intravenously or subcutaneously at a fixed dose of 75mg/m^2/day for 7 consecutive days, (allowing interruptions for weekends, and holidays)

of each 28-day cycle

8. Ascorbic acid will be administered orally daily at 1 g/day for a total of 28 days of each 28 days cycle.

#### **End of Treatment (EOT)**

1. Documentation of frequency of transfusions (only PRBC and Platelets) prior to start of each new cycle
2. Documentation in the medical record of any grade 3 or higher adverse events at each visit. For guidelines on SAE Reporting and AE entry for Case Report
3. ECOG performance
4. Hematology exams (Appendix VI)
5. Serum Chemistry (Appendix VI), including Creatinine, bilirubin, ALT or AST
16. Optional bone marrow aspirate and/or biopsy to confirm response, to be performed at the end of cycle 6. All bone marrows samples are to be stored at Cleveland Clinic

## 11.2 Calendar

Period	Screening Period (Day-17 to Day -3)	Treatment Period														Extended Treatment Period Cycles	End Of Treatment (EOT)	Follow up k
		Cycle 1				Cycle 2		Cycle 3		Cycle 4		Cycle 5		Cycle 6				
Day		-3	1	7 c	14 n	1	7 c	28 g	1	7 c								
Administration of Azacitidine			X	X b		X	X b		X	X b								
Ascorbic Acid Dispensement		X a				X		X		X		X			X			
disease history and prior therapies	X																	
Record RBC/ platelets transfusion	X	X				X		X		X		X		X	X	X		
History and physical exam dm	X	X				X		X		X		X		X	X			X j
Vital signs d	X	X	X	X		X	X	X	X	X	X	X	X	X	X	X		X j
ECOG performance status em	X	X				X		X		X		X		X	X			X
Hematology dm	X	X				X	X	X	X	X	X	X	X	X	X	X		X j
Serum Chemistry d m	X	X				X		X		X		X		X	X			X
Pregnancy test	X														X			
Disease response assessment f	X														X	X		X
Bone marrow biopsy and aspiration L	X														X h			X i
Mutational analysis blood draw L	X l														X			
Methylation profile blood draw L	X		X	X	X													
Drug Diary Accountability		X				X		X		X		X		X	X	X		
Survival Follow up																		X k
Record adverse events m			↔ X →															

- A: For Cycle 1 only, patient will begin treatment with Ascorbic Acid 3 days prior to initial treatment of Azacitidine
- B: Azacitidine administration has a +/- 3 day window to account for breaks in treatment for weekends, and holidays
- C: Day 7 has a +/- 3 day window to account for breaks in treatment for weekends, holidays, and institutional standards
- D: See Appendix VI for required tests
- E: See Appendix I for performance status grading
- F: See Section for 12.0 for MDS/AML response assessment criteria
- G: If patient is eligible for the extended treatment period, and moving forward on the next cycle without a dosing delay, the C6D28 visit can serve as the visit of C7D1. If the patient is not eligible for the extended treatment period the patient's C6D28 visit can serve as the EOT visit.
- H: The cycle 6 bone marrow biopsy can occur up to 14 days (C6D14) prior to the C6D28 visit.
- I: EOT bone marrow biopsy is optional per discretion of the treating physician
- J: These tests in follow up are optional pending discretion of the treating physician
- K: Survival Follow Up will occur bimonthly (60 days +/- 7 days) for a duration of 1 year from patient's EOT visit.
- L: 10 mL of whole blood or bone marrow aspirate whichever available will be collected in extra lab tube for these tests.
- M: If these procedures require a physician visit, these can occur 3 calendar days prior to the day 1 of that cycle (window of - 3 days).
- N: Cycle 1 Day 14 has a +/- 1 day window to account if the day falls on a holiday or weekend.

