#### **3.2 Expected Duration of Treatment and Subject Participation**

Upon signing consent, patients will be enrolled onto the study. Patients will undergo a screening period. The screening period is defined as the time period between the signing of the consent to the day the patient receives the first dose of study drug. During this period the patient will be assessed to determine if the patient meets all inclusion and exclusion criteria to be eligible for the study (Appendix IV).

The treatment period is defined as the time between first day of study drug dosage (Day - 3) to C6D28. At this time the patient will be assessed and eligible to move into the Extended Treatment Period (ETP). The extended treatment period is defined as C7D1 to the patient meets EOT criteria (Section 6: Table 1; Appendix IV)

Study treatment is defined as the treatment period and if applicable the extended treatment period (Appendix IV). Study drug will be continued during the duration of the study treatment unless patients exhibit any EOT criteria (Section 6: Table 1; Appendix IV).

Treatment should be continued for at least 6 cycles in the absence of toxicities that require discontinuation and/or any EOT criteria (Section 6: Table 1; Appendix IV). After 6 cycles of treatment, a bone marrow biopsy and aspiration will be obtained to evaluate response. If patient has achieved either of the below response criteria (Appendix IV) based on their disease diagnosis patient will be eligible continue onto the extended treatment period (ETP). The patient is eligible to remain on treatment during the ETP until disease progression or patient meets EOT criteria (Section 6: Table 1; Appendix IV).

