#### Response Criteria for extended treatment eligibility

- complete remission, partial remission, or hematologic improvement (CR/PR/HI) per IWG 2006 criteria for patients with MDS
- (CR/PR/marrow CR) per IWG 2003 criteria for patients with AML
- If the response is stable disease and the investigator determines the patient is gaining clinical benefit, patient may continue on treatment until progression.

At the point in which the patient meets the any EOT criteria (Section 6) the patient will enter into the follow up period to follow for survival status. The patient will be followed for up to 1 year and/or death, whichever were to occur first. End of study (EOS) is defined as the time the patient completes 1 year of survival follow up and/or patient's death, whichever were to occur first.

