#### **6.4 Criteria for Removal from Study Treatment (EOT)**

In the absence of treatment delays due to adverse events, treatment may continue for 6 cycles or be extended after 6 cycles unless 1 one of the following criteria applies:

End of Treatment Criteria

• Disease progression defined as no response after 6 months of treatment or loss of response during treatment as defined in section 12

• Intercurrent illness that prevents further administration of treatment

• The investigator and/or treating physician considers it to be in the best interest of the subject to permanently discontinue study treatment

○ This includes if the treatment is deemed to be of excessive toxicity to the patient by the treating physician

• Patient decision to withdraw from treatment (partial consent) or from the study (full consent)

• Pregnancy during the course of the study for a child-bearing participant

• Death

• Unacceptable adverse events defined as following:

○ Unacceptable treatment related toxicity, NCI CTC AE version 4.0 Grade 3 or 4 that fails to recover to baseline or < Grade 3 in the absence of treatment within 4 weeks

○ Any toxicity or other issue that causes a delay of study drug administration by more than 4 weeks

Table 1: End of Treatment Criteria

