#### **6.5 Duration of Follow Up**

The clinical course of each adverse event will be followed until resolution, stabilization, or until it has been determined that the study treatment or participation is not the cause.

Serious adverse events that are still ongoing at the end of the study period will necessitate follow-up to determine the final outcome. Any serious adverse event that occurs after the study period and is considered to be possibly related to the study treatment or study participation will be recorded and reported immediately.

Following completion of active treatment (EOT) and while still on study (Follow up), patients will be followed for survival as of standard of care for up to 1 year. This follow up can either be done as a visit to the study doctor's clinic or via telephone call to the patient.

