**Definition of secondary outcomes/endpoints:**

1. Incidence of adverse events of the combination defined by CTCAE 4.1 criteria.  
Toxicity will be any drug related Grade 3 or 4 toxicity.
2. Response duration to the combination recorded from start of treatment to progression
3. Overall survival measured from start of treatment to death or last follow up

**Sample size justification and study design:** The study sample size was determined using Minimax Simon's two-stage design (Simon, 1989. The null hypothesis that the true response rate is 0.3 will be tested against a one-sided alternative that the true response rate is 0.5. In the first stage, 12 patients will be accrued. If there are 3 or fewer responses, the study will be stopped. Otherwise, 16 additional patients will be accrued for a total of 28. The null hypothesis will be

rejected if 11 or more responses are observed in 28 patients. This design yields a type I error rate of 0.1 and a power of 0.8 when the true response rate is 0.5.

**Analysis plan:** Descriptive statistics will be used for the primary endpoint and secondary endpoints 1,2, and 3. Overall survival will be estimated with Kaplan Meier method and will be compared to the survival of a historical cohort of MDS patients treated at our institution with single agent Azacitidine between 2006-2012 using a one-sample log rank test. A Cochran-Mantel-Haenszel test will be used to test for differences in response rate by mutational status controlling for treatment. Unadjusted and adjusted logistic regression models were used to predict response to therapy. Models will be adjusted for covariates including age, sex, and other prognostic factors. The odds ratio (OR) and 95% confidence intervals (CI) will be estimated for the risk group (mutated) and compared with the reference group (WT).

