#### **APPENDIX IV: STUDY DESIGN TIME POINT DEFINITIONS**

Study Time Points	Definitions
Screening	Screening will occur from the time of the consent until day -4
Baseline/Enrollment	Days -17 b to Day -3 c
Treatment Period	Day 1 c to C6D28 or patient meets end of treatment criteria before completing 6 cycles
Extended Treatment Period (ETP)	The extended treatment period is defined as C7D1 to the patient meets EOT criteria
Study Treatment	The treatment period and if applicable the extended treatment period
End of Treatment (EOT)	The day patient meets the defined EOT criteria (Table 1) and discontinues study treatment.
Follow up	Patient will be followed bimonthly (60 days +/- 7 days) for a duration of 1 year after study
End of Study (EOS)	The time the patient completes 1 year of survival follow up and/or patient's death, whichever were to occur first.

A: Day 1 is defined as first dose of Azacitidine  
B: Day -17 is defined as 14 days prior to first dose of study Drug (Day -3)  
C: Day -3 is defined as day of Study Drug

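### Survival follow-up ends 1 year after each patient's own end of treatment, so overall survival beyond 12 months is open to informative censoring

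*Combined protocol and SAP*

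**What the plan says.** Four places set the length of survival follow-up.

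- Section 3.2, on patients who have met an EOT criterion: "The patient will be followed for up to 1 year and/or death, whichever were to occur first".
- Section 6.5, after active treatment: "patients will be followed for survival as of standard of care for up to 1 year".
- Section 11.2, footnote K, ties the clock to the individual: "Survival Follow Up will occur bimonthly (60 days +/- 7 days) for a duration of 1 year from patient's EOT visit".
- Appendix IV defines end of study as: "The time the patient completes 1 year of survival follow up and/or patient's death, whichever were to occur first".

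The clock starts at EOT. Table 1 in Section 6.4 lists among the EOT criteria "Disease progression defined as no response after 6 months of treatment or loss of response during treatment", together with toxicity, intercurrent illness, withdrawal, physician decision and death. For patients who qualify for extended treatment, Section 3.2 says: "The patient is eligible to remain on treatment during the ETP until disease progression or patient meets EOT criteria". Section 3.2 and Appendix V also let stable-disease patients continue if the investigator sees clinical benefit.

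Section 14 measures overall survival (OS) from start of treatment to death or last follow-up. It estimates OS by Kaplan-Meier and compares it with a "historical cohort of MDS patients treated at our institution with single agent Azacitidine between 2006-2012 using a one-sample log rank test". It gives no common cut-off, no truncation time and no analysis for dependent censoring.

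**The concern.** A patient's maximum follow-up is time on treatment plus 12 months. Time on treatment is itself an outcome: patients who fail early leave observation early, and patients who keep responding stay in it. Kaplan-Meier and the one-sample log-rank test both treat a censored patient as having the same future risk as patients still followed at that time. That is doubtful when those censored are mostly treatment failures and those who remain are mostly responders.

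OS against a historical azacitidine cohort is the third secondary objective. The only azacitidine survival figure in the protocol is a median of 24.5 months (Section 1.1). If survival here is similar, the median falls in the part of the curve where this censoring operates.

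**Working it through.** The plan states no OS figure, power or event count, so there is nothing to reproduce. The follow-up rule, EOT criteria, test and n = 28 come from the protocol. The survival, response and time-on-treatment values below are assumptions.

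**Step 1. When censoring starts.** Censoring time = time on treatment + 12 months.

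- Stops at month 1: 1 + 12 = 13 months.
- Stops at the end of cycle 6: 6 × 28 = 168 days, 168 / 30.4 = 5.5 months; 5.5 + 12 = 17.5 months.
- Responder treated for a further 12 months: 17.5 + 12 = 29.5 months.

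The rule censors nobody before 12 months, so it cannot bias the curve up to that point.

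**Step 2. Kaplan-Meier at 24 months, by hand.** Assume 40% respond (median OS 24 months), 15% stop in months 1 to 5 (median 6), and 45% stop at month 6 (median 9, censored at 18). Within each group S(t) = 2^(−t/median).

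- True S(18) = 0.40 × 0.595 + 0.15 × 0.125 + 0.45 × 0.250 = 0.369.
- True S(24) = 0.40 × 0.500 + 0.15 × 0.0625 + 0.45 × 0.1575 = 0.280.
- Kaplan-Meier at 18 months is about 0.369 + 0.005 = 0.374; the 0.005 is the simulated effect of censoring early stoppers at 13 to 17 months.
- After 18 months only responders are under observation, so the curve is multiplied by 2^(−6/24) = 0.841. Kaplan-Meier at 24 = 0.374 × 0.841 = 0.315.
- Bias = 0.315 − 0.280 = about +3.4 points.

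With a median of 15 months in the month-6 group, true S(18) = 0.4525 and S(24) = 0.358. Kaplan-Meier is (0.4525 + 0.005) × 0.841 = 0.385, a bias of +2.7 points.

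**Step 3. Simulation over a range.** With 40–45% responders (median OS 24–36 months, median 12 further months on treatment) and a month-6 group with median OS 9–15 months, the bias is 0 at 12 months, about +0.5 points at 18 and +2.7 to +3.8 at 24. Expected deaths are E = Σ −ln S(xᵢ), where xᵢ is each patient's follow-up time and S is the true survival, taken as the comparator. Observed/expected (O/E) is 0.93 to 0.96. With about 17 observed against 18 expected, the shift is (17 − 18)/√18 = −0.24 SD; across scenarios it is 0.2 to 0.3 SD towards the combination.

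**Step 4. What the direction depends on.** In a second model the death hazard after EOT is R times the on-treatment hazard, median OS is set at 24.5 months, and true survival equals history:

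| R | Response rate | True S(24) | Kaplan-Meier S(24) | O/E, fully followed history | O/E, history with same rule |
|---|---|---|---|---|---|
| 0.5 | 30% | 0.507 | 0.480 | 1.03 | 1.00 |
| 1 | 30% | 0.508 | 0.508 | 1.00 | 1.00 |
| 3 | 30% | 0.508 | 0.541 | 0.93 | 1.00 |
| 5 | 30% | 0.509 | 0.552 | 0.90 | 1.00 |
| 3 | 50% | 0.509 | 0.536 | 0.91 | 1.00 |
| 5 | 50% | 0.510 | 0.546 | 0.87 | 1.00 |

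Over R = 2 to 10, a nominal one-sided 5% test rejects in 5.7% to 16.0% of trials, against 3.7–3.8% at R = 1.

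**Step 5. The comparator's make-up.** The cohort is MDS; Section 4 admits AML, including relapsed or refractory disease. If 20–40% of patients have AML with 1.5 to 2 times the hazard (assumed), O/E at R = 3 is 0.99 to 1.24.

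**Step 6. Does the repair work?** Following everyone to 24 months from start of treatment gives O/E 1.000 in every scenario and rejection in 3.5% to 4.2% of trials. Cutting the present plan at 12 months also gives O/E 1.000.

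**The case against.** A reader might infer that the historical comparison as a whole favours the combination. The documents do not support that. They give no survival by reason for stopping, and EOT also covers withdrawal and physician decision, so a higher hazard after EOT is an assumption. They do not state the cohort's follow-up rule, and under the same rule O/E returns to 1.00. An MDS-only comparator for a trial that includes AML can push the other way by as much or more. What stands is that an opposing bias of unknown size does not remove this one.

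A reader might also infer that every patient without a response is censored by month 18. Section 3.2 and Appendix V allow stable-disease patients to continue, whereas Table 1 in Section 6.4 counts no response after 6 months as an EOT criterion; these passages must be reconciled. If half of the month-6 group continues for a median of 6 more months (assumed), the 24-month bias falls to about +1.7 to +2.5 points. It shrinks but does not vanish.

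The effect is also small against the trial's precision. Even with no censoring, the standard error at 24 months is about √(0.28 × 0.72 / 28) = 0.085, or 8.5 points, and only about 4 to 6 of 28 patients would still be at risk. That is fair and limits the weight of the point. It does not excuse a systematic error that a few calls can prevent.

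**Conclusion.** The point holds in conditional form. Follow-up length depends on outcome by design, so OS beyond 12 months is exposed to informative censoring that Section 14 does not address. If prognosis worsens after EOT, the likely size is about +0.5 points at 18 months and +2 to +4 points at 24 months. O/E is then about 0.93 to 0.96 when true survival equals the comparator, roughly one death too few in 18. Steeper assumed hazards after EOT give more. OS up to 12 months is unaffected by this rule. So is ORR, which makes this a matter for a secondary endpoint: worth correcting, but no threat to the main conclusion.

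**What to change.** Amend Sections 3.2 and 6.5, footnote K of Section 11.2 and Appendix IV so that vital status is collected, by telephone or chart, for every patient to the same fixed time from start of treatment (for example 24 months) or to one pre-set calendar date, whatever the EOT date. A cut-off set at 1 year after the last patient's EOT would not serve, because extended treatment is open-ended and that date has no limit. In Section 14, censor OS at the chosen point, state the historical cohort's follow-up rule and apply the same truncation to it.

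The cost is some extra telephone or chart checks for early leavers among at most 28 patients; Section 6.5 already allows telephone contact.

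If this is not done, limit the OS comparison to the first 12 months from start of treatment and label later Kaplan-Meier estimates as subject to informative censoring. That needs only wording, but gives up about 30% of deaths in the Step 3 scenarios and everything beyond 12 months, including the region of the 24.5-month azacitidine median.

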## **12.0 MEASUREMENT OF EFFECT**

The response criteria recommended by the MDS International Working Group 2006. Responses must be verified, documented, and signed at cycle 6 in the local medical record by the local PI. (Patients are considered non evaluable if they have received less than 2 courses of treatment, unless there is clear disease progression.)

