### **14.0 STATISTICAL CONSIDERATIONS**

**Definition of primary outcome/endpoint:** A binary indicator of overall response, defined as achieving CR, PR, or HI) per 2006 IWG criteria for MDS and MDS/MPN overlap and (CR, CRp, CRi, or PR) per 2003 IWG criteria for AML after 6 cycles of treatment

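### Section 12 calls some early-stopping patients non-evaluable, but Section 14 gives no denominator for the reported ORR; if the label is applied there, it removes only non-responders

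*Combined protocol and SAP*

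**What the plan says.** Section 12.0 (Measurement of Effect) gives the evaluability rule: "Patients are considered non evaluable if they have received less than 2 courses of treatment, unless there is clear disease progression". It does not say what the label does in the analysis.

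Section 14.0 defines a binary primary endpoint, with the time point given as "per 2003 IWG criteria for AML after 6 cycles of treatment". Its design paragraph works on accrual and counts: "In the first stage, 12 patients will be accrued", and after 16 more the null hypothesis is "rejected if 11 or more responses are observed in 28 patients". For analysis it says "Descriptive statistics will be used for the primary endpoint and secondary endpoints 1,2, and 3". It names no analysis set and no ORR denominator.

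The timing of the assessment is described in two further places. Section 12.0: "Responses must be verified, documented, and signed at cycle 6 in the local medical record by the local PI". Section 11.1, Treatment Period, item 12: "MDS Response Assessment, assessed by the treating physician occurring at the end of cycle 6 or EOT, whichever occurs first".

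The table of contents lists a section 3.3 on replacing subjects. The body goes from 3.1 (Number of Subjects) to 3.2 (Expected Duration) and has no such section.

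**The concern.** Evaluability here depends on what happens after treatment starts. A patient who dies, stops for toxicity or withdraws during the first course, without clear progression, takes the label. The exception for clear progression does not keep all such patients in. The end-of-treatment table in Section 6.4 lists death, withdrawal, intercurrent illness and toxicity separately from progression; one entry is "Any toxicity or other issue that causes a delay of study drug administration by more than 4 weeks". The same table defines progression as no response after 6 months or loss of response, and a patient who stops before a second course could rarely show either. Section 12.0 defines progression for MDS only after hematologic improvement, and gives no definition for AML.

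The primary objective is to estimate the ORR, and the primary endpoint is analysed descriptively, so the denominator determines the reported figure. If the choice is left until the data are in, an open-label single-arm trial can report either of two rates, one of which omits its early failures.

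**Working it through.** **Inputs.** From Section 14.0: null rate 0.3, alternative 0.5, first stage of 12 with a stop at 3 or fewer responses, 28 in total, rejection at 11 or more, stated type I error 0.1 and power 0.8. From Section 12.0: the label for fewer than 2 courses. Assumed: m, the number of non-evaluable patients, and x, the number of responders.

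**1. The plan's own figures.** The probability of rejecting is the sum over first-stage counts x1 = 4 to 12 of P(X1 = x1) × P(X2 ≥ r − x1), with X1 ~ Bin(12, p) and X2 ~ Bin(16, p).

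| Reject at | p = 0.3 | p = 0.5 |
|---|---|---|
| ≥ 11 of 28 (printed) | 0.169 | 0.868 |
| ≥ 12 of 28 | 0.095 | 0.802 |

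The stated 0.1 and 0.8 reproduce at ≥ 12, not at the printed ≥ 11. That is a separate matter, and nothing below about the ORR depends on it.

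**2. Effect on the Simon decision.** Both cut-offs are counts of responses in a fixed number of accrued patients. A non-evaluable patient adds nothing to the count, exactly as a non-responder does. Applying the label without replacement or rescaling leaves the decision unchanged.

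**3. Effect on the reported ORR.** Under the 6-cycle definition, each labelled patient is a non-responder. With x fixed, leaving out m of them changes x/28 to x/(28 − m), a ratio of 28/(28 − m). The rate cannot fall, and it is unchanged only if x = 0 or m = 0. For x = 12, with exact (Clopper-Pearson) 95% intervals that ignore the two-stage design:

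| m | ORR | 95% interval |
|---|---|---|
| 0 | 12/28 = 42.9% | 24.5 to 62.8 |
| 2 | 12/26 = 46.2% | 26.6 to 66.6 |
| 4 | 12/24 = 50.0% | 29.1 to 70.9 |

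**4. The early end-of-treatment reading.** If a response recorded at an early end-of-treatment visit counts, as item 12 of Section 11.1 would allow, a labelled patient could be a responder. With m = 2 and one of the two a responder, 12/28 = 42.9% becomes 11/26 = 42.3%, so the direction reverses. Such cases should be few: hematologic improvement must last at least 8 weeks (Section 12.0), and the end-of-treatment marrow is optional (Section 11.2, note I). The documents do not rule them out.

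**5. Power, if 0.5 was meant for evaluable patients.** With an assumed 10% non-evaluable, the rate among all treated is 0.50 × 0.90 = 0.45. The formula in step 1 then gives power 0.63 at ≥ 12 (against 0.80) and 0.74 at the printed ≥ 11 (against 0.87).

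**The case against.** The strongest reply is that Section 14.0 already counts responses in 28 patients, which points to 28 as the intended denominator, and that no text expressly removes anyone. Both parts are true. The first protects the hypothesis test. It does not settle the descriptive ORR, because the usual purpose of calling a patient non-evaluable for response is to take that patient out of the response-rate denominator, and nothing in Section 14.0 overrides the label.

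Three stronger readings are tempting and are not supported:

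- *The reported ORR is biased as the plan stands.* The bias arises only if the label is applied to the denominator, and the plan does not say that it is.
- *The type I error is inflated.* That would need replacement of non-evaluable patients or rescaled cut-offs. The documents state neither.
- *The more patients are lost early, the higher the reported ORR.* Early loss can also remove patients who would have responded, which lowers x. What grows with m, for a given x, is the gap between the two rates.

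It is also fair to say that the intervals for m = 0 and m = 4 overlap heavily, and that 0.5 is the alternative used for power, so an observed ORR of 50% triggers nothing.

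**Conclusion.** The point holds in conditional form. The plan carries a post-treatment evaluability label with no stated use, and a primary estimate with no stated denominator. If the label is used for that denominator, the ORR for a given number of responders is multiplied by 28/(28 − m): with 12 responders, a rise of 3.3 percentage points for m = 2 (46.2 − 42.9) or 7.1 for m = 4 (50.0 − 42.9, from unrounded rates). This rests on an assumed m and on the 6-cycle definition being the operative one; under the early end-of-treatment reading the direction is no longer certain. The go/no-go decision is untouched as written. The plan should be corrected, because the figure at issue is the trial's primary estimate.

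**What to change.** Add to Section 14.0, for example:

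> The primary ORR, like both Simon counts, uses all patients who start study treatment, defined as [the first dose that counts]. Patients without a documented response at the primary endpoint time, including those given fewer than 2 courses, count as non-responders and are not replaced. The ORR in patients evaluable under Section 12 is a sensitivity analysis.

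The first dose needs naming because ascorbic acid starts three days before azacitidine.

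The sponsor should also:

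- state which population the 0.3 and 0.5 rates describe, since the documents do not say;
- reconcile the time point in Section 14.0 and the sign-off in Section 12.0 with item 12 of Section 11.1, and state whether a response documented at an early end of treatment counts in the primary ORR.

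The cost is a few sentences and one alignment of wording, with no new data. The reported ORR may be lower than under an evaluable-only analysis. If 0.5 was meant for evaluable patients, power against the all-treated rate is lower than stated, as in step 5 of the working.
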